**Overall Design:**

This is a 1:1 randomized, open-label phase 3 study in advanced cHL participants  $\geq 18$  years old who are relapsed refractory or ineligible for autologous stem cell transplant (ASCT). Patients will be balanced in the 2 groups in regards to prior therapies. Approximately 340 participants will be treated in one of two arms: 1) nivolumab 360 mg IV every 3 weeks until progression or unacceptable toxicity (except for patients in CR who can discontinue at 2 years) plus BV 1.8 mg/kg IV every 3 weeks for 16 cycles, or until progression or unacceptable toxicity, whichever occurs first or 2) BV alone 1.8 mg/kg every 3 weeks for 16 cycles, or until progression or unacceptable toxicity, whichever occurs first. Treatment may also be discontinued if the participant meets other criteria for discontinuation of study drug outlined in [Section 8.1](#) of the protocol. Participants receiving nivolumab who achieve CR may discontinue treatment after a maximum of 2 years of therapy, provided that there is no prohibitive toxicity. Participants can be BV- naïve, or can have prior BV treatment as a single agent or in combination in any line of therapy. Randomization stratification will be performed on the following two factors: 1) Prior ASCT status (YES/NO). 2) Prior BV use (YES/NO). Participants will be balanced based on the stratification factors per arm.

Participants will undergo screening evaluations to determine eligibility within 28 days prior to first dose. Each 21-day dosing period will constitute a cycle.

Study visits and endpoint measurements will occur as indicated in [Table 2-1](#) though [Table 2-3](#) in the protocol.

Any participant who discontinues the study treatment prior to progression will be followed for progression, then survival, in the follow up phase of the study.

[figure not shown]
As of 17-Oct-2019, enrollment in this study was stopped at the decision of the Sponsor. For currently enrolled participants, at the investigator's discretion, the same study treatment can be continued if the participant is considered to have clinical benefit. Assessments of efficacy and safety will continue per protocol; however, efficacy assessments will be done by investigator.

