**Table 2-2: Procedural Outline During the Treatment Period (CA209812)**

Procedure	Cycle 1 Day 1 - Disease Progression or Unacceptable Toxicity	Notes  All windows proposed are calendar days. Procedures must be done within 72h prior to dosing unless otherwise specified. Dosing is to be performed every 3 weeks
Safety Assessments		
Targeted Physical Examination	X	Lymph node areas (for example, but not limited to, submandibular, cervical, supraclavicular, axillary, or inguinal lymph node), and abdominal organs (eg, spleen, liver)
Vital Signs	X	Includes body temperature, respiratory rate (RR), and seated blood pressure (BP) and heart rate.
Physical Measurements	X	Within 72 hours prior to dosing. Includes Weight and ECOG performance status ( Appendix 7 )
Adverse Events Assessment	Continuously	See Appendix 2/Section 9.2 . Assessed using NCI CTCAE v. 4.03.
Serious Adverse Events Assessment	Continuously	See Appendix 2/Section 9.2 . Assessed using NCI CTCAE v. 4.03
Review of Concomitant Medications	X	See section 7.7
Laboratory Tests	X	Within 72 hours prior to dosing to include CBC w/differential, AST, ALT, ALP, TBili, BUN or serum urea level, creatinine, Ca, Mg, Na, K, Cl, phosphate, LDH, glucose, amylase, lipase, c-reactive protein, albumin
Thyroid Function Testing	See note	TSH (reflex to free T3 and free T4 if abnormal result) to be performed every 9 weeks ( $\pm$ 7 days) from first dose regardless of dosing schedule.
Pregnancy Test for WOCBP	X See note	Serum or urine within 24 hours prior to first dose and then at least once every 4 weeks ( $\pm$ 7 days) regardless of dosing schedule.
Efficacy Assessments		
Radiographic Tumor Assessment FDG-PET-CT or PET-MRI scans from vertex to toes	See note	FDG PET-CT or PET-MRI will be performed at the end of cycle 5, 10, 15, and every 5 cycles until disease progression. FDG PET-CT or PET-MRI can be performed as clinically warranted for suspicion of recurrence during the non-protocol specified time points
B symptoms	See note	Collected Day 1 (prior to dosing) of every other cycle (cycle 1, 3, etc)

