## 7.1 Treatments Administered

Infusions will be performed over a period of once every 3 weeks. Participants should begin study treatment within 3 calendar days of randomization. Participants will be monitored continuously for AEs while on study. Study treatment modifications (eg, dose delay or discontinuation) will be based on specific laboratory and AE criteria (Section 7.4). Doses of study treatment may be interrupted, withheld, or discontinued depending on how well the participant tolerates the study treatment. Treatment with nivolumab will be continued as described in Section 5.1 until disease progression or unacceptable toxicity. Participants treated with nivolumab who achieve a CR may discontinue treatment after a maximum of 2 years of therapy, provided that there is no prohibitive toxicity. Administration of BV should be discontinued after a maximum of 16 cycles, or until disease progression or unacceptable toxicity, whichever occurs first.

All participants who discontinue therapy will be followed through Safety Follow-up Visit 2.

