7.5.1.1 Sensitivity analyses of PFS

Sensitivity analyses of PFS will also be performed as described below. Median PFS, HR (95% CIs), p-value from the log-rank test will be computed as in the primary PFS analysis

- *PFS accounting for assessment after subsequent therapy* participants will be defined similarly to the primary definition except that events (progression or death) and tumor assessments that occurred after subsequent anticancer therapy will be taken into account. A Kaplan-Meier plot will be produced

Table 7.5.1.1-1: Censoring scheme 1 for Sensitivity Analysis of PFS

Situation	Date of Progression or Censoring	Outcome
No baseline tumor assessments	Randomization date	Censored
No on-study tumor assessments and no death	Randomization date	Censored
New subsequent anticancer treatment started without a prior reported progression by BICR or death	Date of last evaluable tumor assessment prior to or on the date of initiation of the subsequent anti-cancer therapy	Censored
Progression per BICR documented at a scheduled or unscheduled visit and no other subsequent anticancer treatment started before progression	Date of the first documented tumor progression	Progressed
Participant progression free, no death and no subsequent anti-cancer therapy treatment started	Date of last evaluable tumor assessment	Censored
Death without prior progression per BICR	Date of death	Progressed

- PFS accounting for missing tumor assessment prior to PFS event (progression or death)*. This analysis will be performed only if at least 20% of events have missing prior tumor assessment. It will apply the following restriction to the primary definition: If the elapsed time between the PFS event and the last on-study tumor assessment immediately prior to the event (or randomization date if no on-study scan) is two or more missed visits (more than 12 weeks + 10 days), the participant will be censored at his last tumor assessment prior to the PFS event (or randomization date if no on-study scan). A Kaplan-Meier plot will be produced.

Table 7.5.1.1-2: Censoring scheme 2 for Sensitivity Analysis of PFS

Situation	Date of Progression or Censoring	Outcome
No baseline tumor assessments	Randomization date	Censored
No on-study tumor assessments and no death	Randomization date	Censored

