New subsequent anticancer treatment started without a prior reported progression by BICR or death	Date of last evaluable tumor assessment prior to or on the date of initiation of the subsequent anti-cancer therapy	Censored
Progression per BICR documented at a scheduled or unscheduled visit and no other subsequent anticancer treatment started before progression	Date of the first documented tumor progression	Progressed
Participant progression free, no death and no subsequent anti-cancer treatment started	Date of last evaluable tumor assessment	Censored
Death without prior progression per BICR and no subsequent anti-cancer therapy treatment started	Date of death	Progressed

Death or progression after two or more missed visits	Date of last tumor assessment prior to the PFS event	Censored
---	---	-----------------

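### The missed-scan sensitivity analysis of PFS uses a 94-day limit although scans are 105 days apart, so progressions found on schedule are censored as if two visits had been missed

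*SAP*

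**What the plan says.** SAP 7.5.1.1 describes two sensitivity analyses of PFS. The second deals with missing assessments before an event. The gap runs back from the event to "the last on-study tumor assessment immediately prior to the event (or randomization date if no on-study scan"). If it amounts to "two or more missed visits (more than 12 weeks + 10 days), the participant will be censored" at that earlier date.

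The analysis is conditional: "This analysis will be performed only if at least 20% of events have missing prior tumor assessment". The SAP does not say how a missing prior assessment is identified for this purpose.

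Table 7.5.1.1-2, which sets out the same scheme, describes the row only as "Death or progression after two or more missed visits" and gives no day count.

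The imaging schedule is in Protocol Table 2-2: "FDG PET-CT or PET-MRI will be performed at the end of cycle 5, 10, 15, and every 5 cycles until disease progression". Scans outside that schedule are allowed and "can be performed as clinically warranted for suspicion of recurrence during the non-protocol specified time points". The protocol fixes the cycle length: "Each 21-day dosing period will constitute a cycle". SAP 2.1 gives the same cycle length.

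**The concern.** A window of 12 weeks plus 10 days covering two visits fits scans 6 weeks apart. No 6-week schedule appears in either document. Here one ordinary interval between scans is already longer than the window meant to represent two missed visits.

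The analysis exists to show whether the PFS result depends on events dated after long unobserved gaps. Applied literally, it would discard progressions found on time. It would keep mainly deaths and progressions picked up at unscheduled scans within 94 days of the previous scan. The PFS curves would be pushed up in both arms, and the result would say nothing about missed assessments. The condition for running it is also affected: if the 20% is judged with the same 94-day limit, the scan schedule alone would normally meet it.

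**Working it through.** **Inputs**
- SAP limit (SAP 7.5.1.1): 12 weeks + 10 days.
- Scan schedule (Protocol Table 2-2): every 5 cycles.
- Cycle length (Protocol 5.1 and SAP 2.1): 21 days.
- Start of treatment (Protocol 7.1): "Participants should begin study treatment within 3 calendar days of randomization".
- BV median PFS (Protocol 3.2): 5.6 months, or 9.3 months with longer follow-up.
- Days per month (SAP 8): 30.4375.

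**1. The SAP's limit and the schedule it implies.** 12 × 7 + 10 = 94 days. If 12 weeks is two visits, the implied interval is 84 / 2 = 42 days (6 weeks).

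**2. The actual interval.** 5 × 21 = 105 days (15 weeks). The excess over the limit with nothing missed is 105 − 94 = 11 days. Neither one interval + 10 days (115) nor two intervals + 10 days (220) gives 94.

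**3. First scan.** Treatment starts 0 to 3 days after randomization, so the first scan falls about 105 to 108 days after it. That exceeds 94, so a progression found there is censored at randomization. Assuming exponential PFS, the share of events arising by day 105 is 1 − 2^(−105 / median in days):
- median 5.6 × 30.4375 = 170.5 days: 1 − 2^(−0.616) = 35%
- median 9.3 × 30.4375 = 283.1 days: 1 − 2^(−0.371) = 23%

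**4. Variation in scan dates.** No scan window is stated, so the widths below are assumptions. Let each scan fall on any whole day within ±w of target with equal chance. A gap between two scans is 94 days or less only if the two deviations shorten it by at least 11 days.

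| w | Ways to shorten by 11 days or more | Share of scan-to-scan gaps over 94 days |
|---|---|---|
| 3 | 0 of 49 | 100% |
| 7 | 4+3+2+1 = 10 of 225 | 95.6% |
| 10 | 10+9+…+1 = 55 of 441 | 87.5% |

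With w = 7 the gap from randomization to the first scan varies at one end only. Its minimum is 105 − 7 = 98 days, still over 94, so every first-scan progression is censored. Weighting by step 3:
- median 5.6 months: 0.348 + 0.652 × 0.956 = 0.97
- median 9.3 months: 0.227 + 0.773 × 0.956 = 0.97

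Simulation under the same assumptions also gives 97%.

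**5. Some progressions found off schedule.** If a share u is found off schedule, spread evenly over the interval, and the rest exactly on schedule, the share censored is (1 − u) + u × 11/105:
- u = 0.25: 0.75 + 0.026 = 78%
- u = 0.50: 0.50 + 0.052 = 55%

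A simulation with the same shares and ±7-day variation gave 77% and 57%. These figures shift by a few points with how unscheduled detection is modelled, and the shares themselves are assumed.

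**6. The SAP's form applied to the real schedule.** 2 × 105 + 10 = 220 days.
- On-time progression: 105 days, stays an event.
- Progression after one missed scan: 210 days, stays an event.
- Progression after two missed scans: 315 days, censored.

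**The case against.** The strongest case is about consequence. Enrollment stopped at 23 of about 340 planned participants, and Protocol 10 rules out formal testing and keeps the planned analyses only where appropriate. SAP 7.1 makes p-values from sensitivity analyses descriptive. The primary PFS analysis does not use this rule. The SAP is version 1.0 from February 2017, still written around central review, and needs updating anyway. All of this stands, and it limits the practical effect. It does not make the rule correct.

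Second, the analysis may never run. If the 20% condition counts assessments truly missed, it may not be met. But once the analysis runs, the 94-day limit still censors on-time progressions.

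Third, a programmer working from Table 7.5.1.1-2 alone would keep on-time progressions as events, because that row counts missed visits and gives no days. That is true, and it means the text and the table give opposite answers for the same participant.

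Fourth, the percentages rest on assumed variation in scan dates. They also assume scanning continues every 15 weeks. BV stops after 16 cycles (16 × 21 = 336 days), and Table 2-3 obtains no further PET scans in participants who stop treatment before progression. Under the exponential assumption, 2^(−336/170.5) = 25% to 2^(−336/283.1) = 44% of events fall after day 336. If the BV-alone arm has no scheduled scans by then, the simulation does not describe those events. The 11-day excess itself needs none of these assumptions.

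Finally, 220 days is not a perfect separator. With ±7-day variation, 10/225 = 4.4% of progressions after a single missed scan would exceed it. That error is small beside the one it replaces.

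**Conclusion.** The concern holds. The limit labelled as two or more missed visits is 11 days shorter than a single scheduled interval. At nominal timing every progression found at a scheduled scan is censored, and those found at the first scan are censored at day 0. With ±7 days of assumed variation, about 97% of scheduled-scan progressions are lost. If a quarter or a half of progressions are found off schedule (assumed), roughly three quarters or somewhat more than half of all progressions are still lost. Deaths and unscheduled-scan progressions within 94 days of the last scan are unaffected.

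The scan schedule is read from Revised Protocol 01. Its summary of key changes describes no change to the on-treatment scan interval, so the mismatch does not appear to come from that revision. The rule should be corrected, but the primary analysis does not depend on it.

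**What to change.** In SAP 7.5.1.1, replace 12 weeks + 10 days with 30 weeks + 10 days (220 days), which is two scan intervals plus the SAP's own 10-day allowance. Put the same figure in the last row of Table 7.5.1.1-2 so that text and table agree. Define the 20% condition with the same window.

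The cost is one line of text, the matching table entry and the derivation program. No new data are needed. In the same edit it would help to state how the rule applies after treatment ends, when Table 2-3 schedules no further scans and a missed visit is undefined.

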7.5.1.2 Consistency of treatment effect on PFS in subsets

To assess consistency of treatment effect on PFS in different subsets, a “forest” plot of the PFS un-stratified hazard ratio (and 95% CI) will be produced for the following variables:

- Prior ASCT status (YES/NO)
- Prior BV use (YES/NO).
- Disease Stage at initial diagnosis (stage 1 or 2, 3, 4)
- Region (US/Canada, Europe, Rest of World).
- Age categorization (<30, ≥30 and <45, ≥45 and <65, ≥65 and <75, ≥75 and <85, ≥ 85)
- Gender (Male, Female).
- Race (White, African American, Asian, and Other).
- ECOG PS (0 vs. 1).
- Smoking status (yes, no, unknown)
- Time from the initial diagnosis to the randomization date (<3 months (yes vs.no))

If a subset category has less than 10 participants (after collapse) per treatment group, HR will not be computed/displayed. Number of events and median PFS along with 95% CI will be displayed for each randomized treatment group.

7.5.1.3 Multivariate PFS analysis

A multivariate analysis using a stratified Cox model will be fitted to assess the treatment effect on OS when adjusted for potential prognostic factors. The stratification factors in the model are the same as the ones in the randomization. The following prognostic factors (source: CRF) will be included in the model in addition to treatment group variable:

- Time from diagnosis to start of the randomization (< 3 months (yes vs. other)).
- Age categorization (< 30, ≥ 30).
- Gender (Male vs. Female).
- Baseline ECOG PS (0 vs. 1).

HR and 95% CI will be provided for treatment variable and all covariates. Descriptive p-values will be provided.

7.5.2 Secondary Efficacy Endpoints

7.5.2.1 CRR

The secondary endpoint CRR based on BICR assessment will be compared in two randomized arms via a two-sided, Cochran-Mantel-Haenszel (CMH) test at 0.05 level stratified by the same factors used in randomization. An estimate of the treatment odds ratio between the nivolumab+BV

and BV arm along with corresponding two-sided 95% CIs and p-value will be presented. An estimate of the difference in CRRs and corresponding 95% CI will be calculated using CMH methodology and adjusted by the same stratification factors.

The estimate of the response rates and associated exact two-sided 95% CIs (by Clopper and Pearson method) will be presented for both arms.

The CRR analysis will be performed at the time of interim and final PFS analysis. A hierarchical testing procedure is employed to control the study-wise type I error at 5%. For more details on the testing procedure, please refer to the interim analysis [section 7.5.4](#).

To assess consistency of treatment effect on CRR in different subsets, a “forest” plot of the unweighted differences in CRR and corresponding exact 95% CI using the method of Newcombe approach will be produced for the same subsets as defined in the primary PFS analysis.

If a subset category has less than 10 participants (after collapse) per treatment group, the differences in CRR will not be computed/displayed.

7.5.2.2 BOR, ORR, TTR, DOR and DOCR

The Best Overall Response (BOR) based on BICR assessment (using 2014 Lugano Classification) will be summarized by response category for each treatment group. ORR as defined as proportion of participants who achieved CR or PR before taking any subsequent anti-cancer therapy, will be computed in each treatment group along with the exact 95% CI using Clopper-Pearson method.

An estimate of the difference in ORRs and Odds ratio and corresponding 95% CIs will be calculated using CMH methodology and adjusted by the same stratification factors as in primary analysis of PFS. A by participant listing of BOR and Tumor Measurements will be provided.

To assess consistency of treatment effect on ORR in different subsets, ORR will be computed across the same subsets as defined in the PFS analysis.

Summary statistics of time to objective response will be provided for each treatment group for participants who achieve PR or CR, as assessed by BICR. To assess tumor response kinetics, time to response will also be analyzed using the KM methodology for all treated participants. Kaplan-Meier curve will represent the cumulative rate of response over time. For the non-responders, time to response will be censored at the maximum time to response + 1 day of all participants in their respective treatment group. Cumulative response rates will be tabulated for Month 6, 12, 18 and 24.

Duration of response in each treatment group will be estimated using KM product-limit method for participants who achieve PR or CR. Median values along with two-sided 95% CI will be calculated. Duration of complete response will be analyzed in a similar manner.

The following participant-level graphics will also be provided by treatment group as randomized:

- For the responders only, time courses of the following events of interest will be graphically displayed: tumor response, tumor progression, last dose received, and death.
- For response evaluable participants, a waterfall plot showing the best reduction in target lesion will be produced.

The CRR, ORR, BOR, DOR and DOCR assessed by investigator will be analyzed similarly to the same endpoints assessed by BICR.

7.5.2.3 OS

The distribution of OS will be compared in two randomized arms via a two-sided, log-rank test stratified (per IVRS) by the same factors in the randomization. The hazard ratio (HR) and the corresponding 95% CI will be estimated in a stratified Cox proportional hazards model using randomized arm as a single covariate. The stratification factors in the model will be the same as the ones in the primary PFS analysis.

The OS curves for each treatment group will be estimated using the Kaplan-Meier (KM) product-limit method. Two-sided, 95% confidence intervals for median OS will be constructed based on a log-log transformed CI for the survivor function $S(t)$.

Survival rates at 6, 12, 18, 24, 36 months may also be estimated using KM estimates on the OS curve for each randomized arm. Minimum follow-up must be \geq timepoint to generate the rate. Associated two-sided 95% CIs will be calculated using the Greenwood's formula for variance derivation and on log-log transformation applied on the survivor function $S(t)$.

The status of participants who are censored in the OS Kaplan-Meier analysis will be tabulated for each treatment group using following categories:

- On-study (on-treatment or in follow-up).
- Off-study (lost to follow-up, withdraw consent, etc.).

To assess consistency of treatment effects in different subsets, a “forest” plot of the OS unstratified hazard ratio (and 95% CI) will be produced for the same subsets as defined in the primary PFS analysis.

7.5.3 Efficacy Analyses for Both PFS and OS

7.5.3.1 Participant Follow-up

The minimum follow-up will be reported. The minimum follow-up is defined as the time interval between the last patient's randomization date and the clinical cutoff date.

The extent of follow-up defined as the time between randomization date and last known date alive (for participants who are alive) or death date (for participants who died) will be summarized descriptively (median, min, max) for all participants randomized.

The currentness of follow-up, defined as the time between last OS contact (i.e., last known date alive or death date) and data cut-off date, will be summarized by treatment group. Participants who died before data cut-off date will automatically have zero value for currentness of follow-up. For participants with last known date alive after data cut-off date, they will have zero value for currentness of follow-up as well. The currentness of follow-up will be categorized into the following categories: 0 days, 1-3 months, 3-6 months, 6-9 months, 9-12 months and ≥ 12 months.

